12 DATA ANALYSIS AND STATISTICAL CONSIDERATIONS

12.1 SAMPLE SIZE

The primary endpoint of the study is the percentage of lesions identified as positive using [¹²³I]mIBG planar scintigraphy which are also identified as positive on [¹²⁴I]mIBG PET/CT. The definition of a positive lesion is described in section 9.1. The aim is to prove that there is more than 90% agreement between the methods, with an expected level of agreement of 97%. Patients are expected to have a median of 3 lesions. Lesions are assumed to be independent within patients for the primary analysis. The following two stage design will be used, where the true proportion of agreement is denoted by P:

In the first stage, a total of at least 9 patients will be recruited, with a combined total of at least 50 lesions positive on [¹²³I]mIBG. Initially an exact one-sided binomial test of the null hypothesis: $P \geq 97\%$ will be done using $\alpha = 0.05$. If this is rejected in favour of the alternative hypothesis $P < 97\%$, the trial will be stopped early for futility. With a total of exactly 50 lesions this will occur if 45 or fewer lesions are also positive on [¹²⁴I]mIBG PET/CT.

If the null hypothesis is accepted, a further one-sided binomial test of the null hypothesis: $P \leq 90\%$ will be done using $\alpha = 0.025$. If this is rejected in favour of the alternative hypothesis $P > 90\%$ then the trial may be stopped early for efficacy. With a total of 50 lesions this will occur only if all 50 lesions are also positive in [¹²⁴I]mIBG PET/CT. If this null hypothesis is not rejected, the trial will continue to the second and final stage.

The second stage will end when an overall total of at least 33 patients with at least 100 lesions have been recruited. An exact one-sided binomial test of the null hypothesis: $P \leq 90\%$ will be done using $\alpha = 0.025$. If this is rejected in favour of the alternative hypothesis $P > 90\%$ then the trial will be declared a success. With a total of 100 lesions this will occur if at least 96 lesions are also positive on [¹²⁴I]mIBG PET/CT.

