12.2 INTERIM AND FINAL ANALYSIS

The interim analysis will be conducted once both of the following conditions are met:

- At least 50 lesions have been identified on [¹²³I]mIBG planar scintigraphy. These lesions will have been identified as positive by a Nuclear Medicine physician at the investigational site.
- A minimum of 9 evaluable patients have completed the study.

The analysis will be done using all identified lesions from at least 9 patients. Therefore, the total number of lesions is expected to be more than 50. The number of lesions identified on [¹²³I]mIBG planar scintigraphy will be reported to the CSM at the CDD at the time of sponsor authorisation of the supply of the [¹²⁴I]mIBG tracer from the manufacturing organisation to the investigational site. The CSM will communicate to the observers and the statistician when the conditions have been met to trigger the interim analysis.

The interim analysis will assess the primary endpoint by comparison of the number of positive lesions detected on [¹²³I]mIBG planar scintigraphy and [¹²⁴I]mIBG PET/CT in order to compare the two modalities. The imaging data will be analysed and scored separately by an agreed number of observers using the same scoring method as described in Section 9.1 in order to prevent subjective bias. Observers may perform their assessment of study imaging data prior to the interim and final

analyses in batches but will remain blinded to the scores of the other observers until the interim and final analyses are triggered and they meet to perform the consensus reviews. Assessment of the reported safety data will be performed at the interim review and will be considered as part of the decision whether to continue recruitment. The feasibility of recruitment of the required minimum number of patients will also be considered in this decision.

The final analysis will be conducted after one of the following conditions is met:

- The study is terminated early
- The end of trial as defined in Section 11 has been reached.

Following lesion detection the agreed number of experienced observers will also perform a semi-quantitative assessment of [¹²⁴I]mIBG PET/CT scans and [¹²³I]mIBG imaging employing SUVmean and SUVmax. The level of disease involvement will be assessed using the International Society of Paediatric Oncology Europe Neuroblastoma (SIOPEN) scoring method and the Curie scoring method (see Appendix 5).

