4.2.3 Tertiary endpoints

4.2.3.1

[REDACTED]

[REDACTED]

[REDACTED]

[REDACTED]

4.2.3.2

[REDACTED]

[REDACTED]

[REDACTED]

4.2.3.3 [REDACTED]

[REDACTED]

4.2.3.4 [REDACTED]

[REDACTED]

4.2.3.5 [REDACTED]

[REDACTED]

4.2.3.6

[REDACTED]

5 Interim Analyses

The interim analysis should be performed at the first available timepoint after no less than 9 evaluable patients have completed both their [¹²³I]mIBG and [¹²⁴I]mIBG scans, and a combined total of at least 50 lesions have been found on [¹²³I]mIBG. At this point the consensus panel should meet to evaluate and record their opinions as soon as practically possible. Once this has been done, the interim analysis can be performed.

Initially an exact one-sided binomial test of the null hypothesis: $p \geq 97\%$ will be done using $\alpha = 0.05$. If this is rejected in favour of the alternative hypothesis $p < 97\%$, the study will be stopped early for futility.

If the null hypothesis is accepted, a further one-sided binomial test of the null hypothesis, $p \leq 90\%$, will be done using $\alpha = 0.025$. If this is rejected in favour of the alternative hypothesis $p > 90\%$ then the trial may be stopped early for efficacy. If this null hypothesis is not rejected, the trial will continue recruitment to the second and final stage.

The results of the interim analysis should be reported to the trial sponsor.

6 Timing of Statistical Analysis

The interim analysis will be performed as detailed in section 5. The final analysis should be performed after all patients recruited to the trial have undergone all scheduled on-trial scans,

7 Data checking plan

All data checking activities will be carried out by the study sponsor before transferring data for analysis. On receipt of data by the study statistician no further formal data checks will be made.

8 Signatures

Study Statistician

_____ Date _____
[REDACTED]

Chief Investigator

_____ Date _____
[name]

ADDENDUM

CCR4051 124ImIBG: Statistical Analysis Plan

Following the statistical report review on 9th November 2020 by the internal and external mIBG Project Team, this addendum has been written to clarify the analysis of the mIBG trial endpoints.

Primary objective	Endpoint	Change in analysis with rationale

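### With an uncapped lesion count, the interim futility test against 97% can stop the trial on data that are on course for, or have already passed, the 90% success test

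*Combined protocol and SAP*

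**What the plan says.** Protocol 12.1 sets the goal: "The aim is to prove that there is more than 90% agreement between the methods, with an expected level of agreement of 97"%. At the interim, an exact one-sided binomial test of the "null hypothesis: $P \geq 97\%$ will be done using $\alpha = 0.05" comes first. On rejection, "the trial will be stopped early for futility. With a total of exactly 50 lesions this will occur if 45 or fewer lesions" show as positive on PET/CT. The only cut-off printed is for 50 lesions.

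The efficacy test is conditional on that result: "If the null hypothesis is accepted, a further one-sided binomial test of the null hypothesis: $P \leq 90\%$ will be done using $\alpha = 0.025". Its printed cut-off is again for 50 lesions: "With a total of 50 lesions this will occur only if all 50 lesions are also positive in" PET/CT. The futility stop is mandatory in wording, while the efficacy stop is permissive.

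SAP 1.4, 4.2.1 and 5 repeat the same order and levels; in SAP 5, "the study will be stopped early for futility" once 97% is rejected. Neither document says which test prevails if a result satisfies both.

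Protocol 12.2 includes every identified lesion from at least nine patients and adds: "Therefore, the total number of lesions is expected to be more than 50". No upper limit is set at either stage. The printed operating characteristics (82% power, alpha 0.03, 22% early efficacy, 57% early futility) are for 50 and 100 lesions.

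**The concern.** Success means showing agreement above 90%. Evidence that agreement is below 97% does not show that this goal is out of reach: a true rate of 94% or 95% fails the first hypothesis and satisfies the second. With few lesions the distinction hardly matters, because only a poor result can reject 97%. With many lesions it does, because a fixed-level test rejects 97% on results that sit comfortably above 90%.

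For a tracer with true agreement in the mid-nineties, more interim data would therefore make a mandatory futility stop more likely. At high enough counts the plan would require a futility stop on data that pass its own efficacy test.

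**Working it through.** **Inputs.** Success bar 0.90, expected rate 0.97, futility level 0.05, efficacy level 0.025 and the 50/100-lesion design come from protocol 12.1. Lesions are treated as independent, as the plan assumes. Final lesion counts other than 100 are my assumptions.

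**Reproducing the plan.** X is the number of lesions also positive on PET/CT.
- Futility at 50: P(X≤45 | 50, 0.97)=0.0168 and P(X≤46)=0.0628, so the cut is ≤45.
- Efficacy at 50: 0.9^50=0.0052 and P(X≥49 | 50, 0.90)=0.0338, so the cut is 50/50.
- Final at 100: P(X≥96 | 100, 0.90)=0.0237 and P(X≥95)=0.0576, so the cut is ≥96.
- Two-stage sums: power 0.8215, type I error 0.0266, early efficacy at 97% 0.218, early futility at 90% 0.569. These match the printed 82%, 0.03, 22% and 57%.

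**At the planned size.** A result of 45/50 leaves at most 45+50=95, below 96, so the futility stop loses nothing. At 60 interim and 110 final lesions, the planned rule and the rule proposed below have the same probability of success.

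**Larger interim counts.** For each n, the futility cut is the largest k with P(X≤k | n, 0.97)≤0.05. The efficacy cut is the smallest k with P(X≥k | n, 0.90)≤0.025. The last column is P(X≤futility cut | n, 0.95).

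| Interim lesions | Futility if ≤ | Efficacy if ≥ | P(futility stop), true rate 95% |
|---|---|---|---|
| 50 | 45 | 50 | 10% |
| 100 | 93 | 96 | 23% |
| 150 | 141 | 143 | 34% |
| 200 | 189 | 189 | 42% |
| 300 | 285 | 281 | 54% |

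**Overlap.** The two regions share at least one result at 180–182 lesions and at every count checked from 193 to 399.
- 189/200: P(X≤189 | 0.97)=0.040 and P(X≥189 | 0.90)=0.017.
- 285/300: P(X≤285 | 0.97)=0.039 and P(X≥285 | 0.90)=0.0013.

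**Before the overlap.** At 141/150 with an assumed final count of 300, the final cut is 281, so 281−141=140 of the next 150 are needed. At the observed rate of 141/150=0.94, P(Bin(150, 0.94)≥140)=0.71. With other final sizes it is 0.57 (72 more lesions, that is 24 patients with 3 each) or 0.96 (550 lesions, that is 150×33/9).

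Conditional power at the boundary and observed rate first exceeds 50% at 101 interim lesions (always from 112) if the final count is n×33/9. With 72 further lesions it does so at 134 (always from 146).

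**Probability of overall success at a true rate of 95%** (planned rule, then proposed rule; final sizes assumed): 0.444 and 0.444 at 50/100; 0.666 and 0.733 at 100/200; 0.653 and 0.890 at 150/300; 0.583 and 0.971 at 200/400.

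**The case against.** Stopping when the design alternative is rejected is a recognised futility approach. It costs at most 5% at the 97% for which the trial was powered. The 95% scenario is mine, and there even the 50/100 design succeeds only 44% of the time. The plan expects a median of 3 lesions and about 100 lesions from 33 patients, and SAP 5 calls the interim at the first opportunity after both triggers are met. An overlap needs at least 180 interim lesions, a mean of 180/9=20 per patient with nine patients. All of this stands, and it limits where harm begins.

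It does not settle the matter, because a median does not bound a mean and the count is uncapped. Fifty lesions from nine patients is already 5.6 each. SAP 2.1 plans a sensitivity analysis in patients with under 10 lesions, and the SAP addendum separates those with under 20, so patients with heavy lesion loads are foreseen.

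It can also be said that the data would not simply be labelled futile. Protocol 12.2 calls for a final analysis after early termination, and 12.2.1 tests against 90% at 0.025. That is correct, but it means that 189/200 would stop for futility and then be declared significant, which is a contradiction the plan should not leave open. The synopsis and protocol 3.3 describe early efficacy as all lesions agreeing; read literally, that would never overlap with futility, but it is not the test in 12.1.

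A reader might infer that any interim above 50 lesions stops trials that would probably succeed. The figures do not support that. For example, 45/50 has 79% conditional power with 183 final lesions, and 93/100 has 82% with 200, only if the true rate is the 97% just rejected. At the observed rates these are 0.7% and 16%. The 45/50 result would also stop under the rule proposed below.

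**Conclusion.** The point holds in a limited form and should be fixed. A mandatory futility test against 97%, at fixed level and ahead of the efficacy test, is harmless at or near 50/100 lesions. It becomes costly somewhere above about 100 interim lesions, depending on the final size. From 180–182, and again from 193, it can override a met efficacy criterion. At a true rate of 95% the chance of a futility stop rises from 10% at 50 lesions to 42% at 200.

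The cut-offs and overlap are exact under the plan's independence assumption. The conditional powers and overall success probabilities also depend on assumed final counts. The documents do not show that such large interim counts are likely, only that nothing excludes them. Nor do they support saying that the rule is coherent only at exactly 50 and 100 lesions.

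**What to change.** In protocol 12.1 and SAP 1.4, 4.2.1 and 5:
1. Run the test against 90% first, so that a met efficacy criterion cannot be overridden.
2. If it is not met, stop for futility only if observed agreement is 90% or less.

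At 50 lesions step 2 is exactly ≤45/50, so the printed 82%, 22% and 57% stay as they are. The two criteria cannot both be met at any count, because a result at or below 90% cannot reject the hypothesis that agreement is at most 90%. The futility rule keeps its function: at a true rate of 90% it stops 57%, 55%, 54% and 53% of trials at 50, 100, 150 and 200 lesions.

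Align the synopsis and protocol 3.3 at the same time. Both stop for futility below 45 of 50, whereas 12.1 stops at 45 or fewer. The printed 57% matches the latter; a cut of ≤44 gives 38%.

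The cost is wording in these places, fewer futility stops at larger counts, and a higher overall one-sided alpha. With assumed final sizes, alpha goes from 0.031 to 0.034 at 100/200, from 0.017 to 0.027 at 150/300, and from 0.008 to 0.034 at 200/400. These should be printed beside the existing 0.03.

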12.2 INTERIM AND FINAL ANALYSIS

The interim analysis will be conducted once both of the following conditions are met:

- At least 50 lesions have been identified on [¹²³I]mIBG planar scintigraphy. These lesions will have been identified as positive by a Nuclear Medicine physician at the investigational site.
- A minimum of 9 evaluable patients have completed the study.

The analysis will be done using all identified lesions from at least 9 patients. Therefore, the total number of lesions is expected to be more than 50. The number of lesions identified on [¹²³I]mIBG planar scintigraphy will be reported to the CSM at the CDD at the time of sponsor authorisation of the supply of the [¹²⁴I]mIBG tracer from the manufacturing organisation to the investigational site. The CSM will communicate to the observers and the statistician when the conditions have been met to trigger the interim analysis.

The interim analysis will assess the primary endpoint by comparison of the number of positive lesions detected on [¹²³I]mIBG planar scintigraphy and [¹²⁴I]mIBG PET/CT in order to compare the two modalities. The imaging data will be analysed and scored separately by an agreed number of observers using the same scoring method as described in Section 9.1 in order to prevent subjective bias. Observers may perform their assessment of study imaging data prior to the interim and final

analyses in batches but will remain blinded to the scores of the other observers until the interim and final analyses are triggered and they meet to perform the consensus reviews. Assessment of the reported safety data will be performed at the interim review and will be considered as part of the decision whether to continue recruitment. The feasibility of recruitment of the required minimum number of patients will also be considered in this decision.

The final analysis will be conducted after one of the following conditions is met:

- The study is terminated early
- The end of trial as defined in Section 11 has been reached.

Following lesion detection the agreed number of experienced observers will also perform a semi-quantitative assessment of [¹²⁴I]mIBG PET/CT scans and [¹²³I]mIBG imaging employing SUVmean and SUVmax. The level of disease involvement will be assessed using the International Society of Paediatric Oncology Europe Neuroblastoma (SIOPEN) scoring method and the Curie scoring method (see Appendix 5).

12.2.1 Statistical Analysis of Primary Endpoint

The proportion of positive lesions detected by routine [¹²³I]mIBG planar scintigraphy which are also identified as positive using [¹²⁴I]mIBG PET/CT will be calculated. An exact one-sided binomial test of the null hypothesis that this proportion is not more than 90% will be performed, using an alpha of 0.025 to define significance.

12.2.2 Statistical Analysis of Secondary Endpoint

The proportion of positive lesions detected by routine [¹²³I]mIBG imaging using 3D SPECT which are also identified as positive using [¹²⁴I]mIBG PET/CT will be calculated. An exact one-sided binomial test of the null hypothesis that this proportion is not more than 90% will be performed, using an alpha of 0.05 to define significance.

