The majority of patients treated for neuroblastoma will have [¹²³I]*m*IBG scintigraphy using 3D SPECT over the chest and abdomen in addition to planar scintigraphy of the full body. The imaging review performed for the assessment of the primary objective will be repeated to read and score lesions identified by the available [¹²³I]*m*IBG SPECT. The number of positive lesions identified by SPECT will be used to meet the secondary objective of comparison of [¹²⁴I]*m*IBG PET/CT with [¹²³I]*m*IBG scintigraphy with 3D SPECT.

The imaging review will then be repeated to read and score all the available conventional imaging taken together including [¹²³I]*m*IBG planar and SPECT scintigraphy and cross sectional imaging with CT and MRI.

[Redacted]

[Redacted]

[Redacted]

[Redacted]

[Redacted]

[Redacted]

[Redacted]

[Redacted]

[Redacted]

[Redacted]

[Redacted]

[Redacted]

[Redacted]

[Redacted]

[Redacted]

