9.2 SECONDARY ANALYSIS

The agreed number of experienced observers will perform the same analysis of [¹²³I]mIBG scintigraphy by 3D SPECT where this was performed as part of the routine imaging for a patient. Using the method described in Section 9.1 the observers will score suspected lesions for this modality. The percentage of positive findings identified on routine [¹²³I]mIBG scintigraphy by 3D SPECT also identified by the novel [¹²⁴I]mIBG PET/CT will be determined.

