2.1 Definition of Analysis Sets

The following trial populations have been defined for reporting purposes:

- Full Analysis Population: All patients enrolled to the study.
- Safety [^{123}I]mIBG Population: All patients who receive [^{123}I]mIBG (these patients may or may not have received [^{124}I]mIBG).
- Safety [^{123}I]mIBG and [^{124}I]mIBG Population: All patients who receive both [^{123}I]mIBG and [^{124}I]mIBG.
- Evaluable Population: Patients who received both [^{123}I]mIBG and [^{124}I]mIBG and underwent trial scanning with both agents. All lesions from these patients are considered independent of one another.
- [REDACTED]
- A sensitivity analysis will be informed in those in the evaluable population and have less than 10 lesions.

The primary analysis set will consist of all patients consented to the study, with at least one positive lesion recorded on routine [^{123}I]mIBG planar scintigraphy, who have also completed [^{124}I]mIBG PET/CT within 3 to 21 days as planned i.e. the Evaluable Population. Patients who did not undergo both [^{123}I]mIBG planar scintigraphy and [^{124}I]mIBG PET/CT will be excluded from this set, as will any patient where zero positive lesions were found on [^{123}I]mIBG planar scintigraphy, and patients with more than 21 days between [^{123}I]mIBG and [^{124}I]mIBG scans.

The safety analysis set for the secondary objective will consist of all patients consented to the study who received any dose of [^{124}I]mIBG at any time whether or not they subsequently completed any of the planned imaging procedures i.e. the Safety [^{123}I]mIBG and [^{124}I]mIBG Population. Additionally, all AEs occurring post consent and prior to [^{124}I]mIBG will be summarised (including those occurring post [^{123}I]mIBG administration).

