2.2 Violations and deviations

Taking the date of [^{123}I]mIBG scan as Day 0, patients whose [^{124}I]mIBG scans takes place on Day 22 or more will be excluded from the primary analysis set, but included in the safety set.

Patients who do not receive the planned injection of [^{124}I]mIBG will not be included in any statistical analysis, however their safety data will be summarised as described in Sections 2.1 and

3 3.1.5. Primary and Secondary endpoints

Each evaluable study patient will be assessed for disease using up to five different modalities:

[^{124}I]mIBG PET/CT (the experimental modality)

[^{123}I]mIBG planar scintigraphy (the primary comparator)

[^{123}I]mIBG planar scintigraphy + SPECT (a secondary comparator)

On each modality (unless otherwise stated), each of the following endpoints is recorded. [^{124}I]mIBG PET/CT and [^{123}I]mIBG planar scintigraphy results will be assessed by an agreed number of observers independently who will record all relevant endpoints as listed below. Prior to the interim analysis, the observers will meet to establish a consensus opinion and record their agreed consensus endpoints for each patient. The same procedure will take place prior to the final analysis, for all scans which had not previously been included in the interim analysis.

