3.1.1 Total number of positive lesions recorded

The total number of lesions will be provided to the Statistician via validated listings from the Sponsor. Data will be recorded in the eCRF by the Trial Manager at the Central Imaging Unit and Source Data Verified (SDV'd) by a Sponsor Clinical Research Associate. The Sponsor Clinical Study Manager will perform a data review before the eCRF is locked and listings are provided to the Statistician.

In summary, the following data will be provided to the Statistician for each evaluable patient for each imaging modality as calculated by each individual Reviewer and as a consensus:

- Number of lesions in each skeletal segment and total number of lesions using the CURIE method (i.e. all lesions with a score of 4 or 5) and also:
 - Total number of lesions with a confidence score of 1
 - Total number of lesions with a confidence score of 2
 - Total number of lesions with a confidence score of 3
 - Total number of lesions with a confidence score of 4
 - Total number of lesions with a confidence score of 5
- Number of lesions in each skeletal segment and total number of lesions using the SIOPEN method (i.e. all lesions with a score of 4 or 5) and also:
 - Total number of lesions with a confidence score of 1
 - Total number of lesions with a confidence score of 2
 - Total number of lesions with a confidence score of 3
 - Total number of lesions with a confidence score of 4
 - Total number of lesions with a confidence score of 5

For example, one Patient's PET/CT scan will have the data above provided but as three or more sets (for detail of the number of reviewers, see the Imaging Review Manual):

- Reviewer 1's data set
- Reviewer 2's data set
- Consensus data set

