4.2 Analysis Methods

4.2.1 Primary endpoint

SIOPEN total numbers of lesions detected on [¹²⁴I]mIBG vs [¹²³I]mIBG will be compared as follows:

In the first stage, a total of at least 9 evaluable patients will be recruited, with a combined total of at least 50 lesions positive on [¹²⁴I]mIBG PET/CT. Initially an exact one-sided binomial test of the null hypothesis: $p \geq 97\%$ will be done using $\alpha = 0.05$. If this is rejected in favour of the alternative hypothesis $p < 97\%$, the study will be stopped early for futility.

If the null hypothesis is accepted, a further one-sided binomial test of the null hypothesis, $p \leq 90\%$ will be done using $\alpha = 0.025$. If this is rejected in favour of the alternative hypothesis $p > 90\%$ then the study may be stopped early for efficacy. If this null hypothesis is not rejected, the study will continue to the second and final stage.

Only if following the interim analysis recruitment is to continue, a second stage will be required and will end when an overall total of at least 33 evaluable patients with at least 100 lesions have been recruited. An exact one-sided binomial test of the null hypothesis, $p \leq 90\%$, will be done using $\alpha = 0.025$. If this is rejected in favour of the alternative hypothesis $p > 90\%$ then the study will be declared a success.

All above tests will be done using the following method: For each patient, the total number of lesions assessed as positive by consensus opinion (with confidence score 4 or 5) on [¹²³I]mIBG planar scintigraphy is referred to as n_{123} , and the total number of lesions assessed as positive by consensus opinion (with confidence score 4 or 5) on [¹²⁴I]mIBG PET/CT is referred to as n_{124} , with the minimum of these two numbers known as n_{\min} . The primary endpoint will be reported by the sum of n_{\min} over all patients, divided by the sum of n_{123} over all patients.

In addition, for each patient the difference and ratios between n_{123} and n_{124} will be calculated and the distribution of these variables will be summarised using the median, upper and lower quartiles. The number and percentage of patients with n_{124}/n_{123} less than 1, equal to 1 and greater than 1 will be reported.

Population to be used: Evaluable population & sensitivity population

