4.2.2 Secondary endpoints

SIOPEN numbers of positive lesions will be compared between [¹²⁴I]mIBG PET/CT vs. [¹²³I]mIBG planar scintigraphy+SPECT, using the same methodology and populations as for the primary endpoint.

The primary analysis and the above secondary analysis will be re-analysed using the CURIE score.

Safety and toxicity, are reported using descriptive statistics and line listings only, using the safety population

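### The SPECT secondary test has two definitions: SPECT-positive lesions at one-sided 0.05 in the protocol, planar+SPECT with the primary's methods and populations and no stated alpha in SAP 4.2.2

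*Combined protocol and SAP*

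**What the plan says.** **Protocol.** Section 12.2.2 puts the lesions positive on 3D SPECT in the denominator and tests the proportion also positive on PET/CT against 90%. The exact one-sided binomial test "will be performed, using an alpha of 0.05 to define significance". Section 9.2 defines the same percentage, with SPECT scored as its own modality "where this was performed as part of the routine imaging for a patient". Section 9.2 itself states no test and no alpha. The synopsis (1.2) describes "scintigraphy using 3D SPECT over the chest and abdomen in addition to planar scintigraphy of the full body" for the majority of patients.

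**SAP body.** The endpoint row in 1.2 names SPECT-positive lesions. Section 3 lists "planar scintigraphy + SPECT (a secondary comparator"). Section 4.2.2 compares PET/CT with planar+SPECT "using the same methodology and populations as for the primary endpoint". It prints no alpha. The primary method in 4.2.1 tests 90% at one-sided 0.025 and counts agreement from two totals per patient, "with the minimum of these two numbers known as" n_min. The Evaluable Population in 2.1 is patients who received both agents "and underwent trial scanning with both agents". SPECT is not required.

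**SAP addendum.** The endpoint is again SPECT-positive lesions, analysed per skeletal segment and separately for soft tissue. Table 1 gives SPECT its own column. The addendum presents itself as a clarification following a statistical report review. It states no alpha, does not withdraw section 3 or 4.2.2, and does not say whether the test is pooled or per segment.

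**The concern.** Three elements of the first secondary test differ or are left open between the texts.

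- **Comparator.** SPECT-positive lesions and planar+SPECT-positive lesions are different denominators. Planar is whole-body, so the combined version admits skull and limb lesions outside the SPECT field. Those planar lesions already serve the primary endpoint. The combined proportion is therefore not the endpoint that the protocol and SAP 1.2 state.
- **Population.** The primary's population does not require SPECT, so patients without it could contribute planar lesions only.
- **Alpha.** Using the primary's methodology may bring in 0.025, or may refer only to the counting rule.

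At stake is the significance claim on the first secondary objective. The choice is also still open in text finalised after a statistical report had been reviewed, which makes it harder to show that the comparator was not chosen on the results.

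**Working it through.** **1. Coverage, from addendum Table 1.** The SIOPEN skeletal rows are skull, thorax, humeri L/R, forearms L/R, spine, pelvis, femora L/R and tibiae/fibulae L/R: 1+1+2+2+1+1+2+2 = 12. Planar is ticked for 12. SPECT is ticked for 3 (thorax, spine, pelvis) and marked x for 12 − 3 = 9. Soft tissue is ticked for both.

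**2. Test used.** The one-sided exact p-value is P(X ≥ x) for X ~ Binomial(n, 0.90), with lesions independent, as both documents assume. As a check on the method, the plan's own primary rule of at least 96 of 100 gives P(X ≥ 96) = 0.0237, below 0.025, while 95 of 100 gives 0.0576. The stated cut-off is reproduced. The documents give no lesion count or power for the SPECT endpoint, so every n below is an assumption.

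**3. Comparator alone, alpha held at 0.05.**

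| SPECT lesions only | p | Planar-only lesions added | Planar+SPECT | p |
|---|---|---|---|---|
| 48/50 | 0.112, fails | 11, all matched | 59/61 | 0.049, passes |
| 49/50 | 0.034, passes | 10, one missed | 58/60 | 0.053, fails |

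Across SPECT totals from 30 to 120 (91 values), a result one lesion short of passing becomes a pass after 1 to 16 extra matched lesions (mean 7.9). In the other direction, take the lowest passing result and add lesions of which one is missed. It becomes a fail at 61 of 91 totals when 5 are added, 29 of 91 when 10 are added, and 0 of 91 when 20 are added. The reverse flip therefore needs few added lesions or more than one miss.

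**4. Alpha alone, 0.05 against 0.025.** Over the same 91 totals the cut-offs differ by exactly one lesion at 59 and coincide at 32. Examples: n=50, 49 against 50; n=80, 77 against 78; n=60, 59 under both; n=100, 96 under both. For n=30 to 35 the 0.025 test cannot reject even with every lesion matched (0.9^35 = 0.02503), while the 0.05 test can. If true agreement is 97%, the chance of landing on the one disputed lesion is 34% at n=50, 21% at n=80 and zero at n=60 and n=100.

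**5. Limit of these figures.** They add individually matched or missed lesions. SAP 4.2.1, which 4.2.2 inherits, takes the smaller of two patient totals, so a PET/CT lesion anywhere in the patient can offset a miss elsewhere. The examples show sensitivity to the denominator; they do not predict what 4.2.2 would count.

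**The case against.** **The objective can be read as planar+SPECT.** Every objective row speaks of scintigraphy with 3D imaging by SPECT, and the synopsis describes SPECT as done in addition to whole-body planar. This is a fair reading of the objective. The endpoint rows and protocol 12.2.2 nevertheless name SPECT, and those define what is tested.

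**Planar+SPECT matches PET/CT's coverage.** Table 1 gives both planar and PET/CT as vertex to feet. Setting whole-body PET/CT totals against SPECT-only totals under the n_min rule would inflate agreement. This stands, and the fix has to restrict the PET/CT counts accordingly.

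**Patients without SPECT may simply drop out.** SAP section 3 speaks of up to five modalities per patient. A reader might infer that such patients will enter with planar lesions only. The text leaves that open without stating it.

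**The SAP's silence on alpha does not contradict the protocol.** Correct. A reader might also infer a settled change from 0.05 to 0.025, but 4.2.2 does not say so, and step 4 shows the effect is small.

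**The test decides little.** Stopping and trial success rest on the primary endpoint alone. This stands and limits the weight of the point.

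**Conclusion.** The conflict is in current text and should be reconciled. Followed as written, SAP 4.2.2 tests a proportion that is not the stated endpoint, because its denominator can include planar lesions from the 9 of 12 skeletal segments marked x for SPECT. The result of the secondary test can change in either direction with the comparator. Alpha is a minor matter of at most one lesion, and of none at n=100.

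The true size cannot be computed. No SPECT lesion count is given, and the figures assume independent, individually matched lesions at illustrative totals. A reader might infer that the trial's conclusion is at risk, or that the addendum has already settled the matter. The documents support neither: no stopping or success rule uses this test, and the addendum points towards SPECT alone without withdrawing 4.2.2.

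**What to change.** Amend SAP section 3 and 4.2.2, and state that the new text replaces the 4.2.2 wording:

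1. The tested comparator is consensus-positive SPECT lesions in patients who had SPECT, against 90%, at the protocol's one-sided 0.05.
2. The test is on one pooled count. State explicitly whether soft tissue is in that count. Per-segment results are descriptive.
3. Take the minimum of the SPECT and PET/CT counts within each patient and segment, using only segments that SPECT covered, so that PET/CT lesions outside the SPECT field cannot offset misses. Label this an approximation. It can count different lesions in one segment as a match, or miss a match when the two modalities assign a lesion to different segments, so it can err either way.
4. Use the existing SPECT-alone reads described in protocol 9.2 and the addendum. SAP 3.1.1 supplies "Number of lesions in each skeletal segment and total number of lesions using the SIOPEN method" for each modality, but section 3 visibly lists only planar+SPECT, so first confirm that SPECT-alone segment counts are held.
5. Keep planar+SPECT as a supporting comparison.
6. If results had been seen when the addendum was written, report the test under both comparators and at both 0.05 and 0.025.

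The cost is one line in section 3 and a short paragraph in 4.2.2; protocol 9.2 and 12.2.2 stay as they are. The downside is fewer lesions, and so less precision, than with planar+SPECT.
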